## 5.5 STRATEGIES FOR RECRUITMENT AND RETENTION

The target sample size is 56 participants with 28 SLPs and 28 OTs. We anticipate one site will be used – UNC Chapel Hill; although the study will be completed virtually by participants. Target enrollment will not be stratified for age, gender, or race/ethnicity for this pilot study, but future studies will control for these variables. Because participants are expected to be practicing in early intervention, participants will be recruited from private practices (which contract with early intervention) and from the early intervention system in North Carolina. Participants will be recruited through web search, the Child Developmental Services Agency, and word of mouth. Potential participants will be emailed through these groups and will be directed to an interest survey where they will complete a screening. If eligible and interested, they will provide their name and email. In the order of entry, the PI will email them a link to the survey.

Because the fields of occupational therapy and speech language pathology are majority female, specific female recruitment is not necessary. For this pilot study, participants will not be specifically selected for race/ethnicity, but this will be pursued in future, larger studies.

Participants who complete the full survey will receive a \$25 gift card as an incentive.

## 6 STUDY INTERVENTION

### 6.1 STUDY INTERVENTION(S) ADMINISTRATION

### 6.1.1 STUDY INTERVENTION DESCRIPTION

The study intervention is a checklist that was developed with feeding specialists at UNC Health through Delphi surveys. The checklist contains four headings: gastrointestinal, nutritional, behavioral, and aerodigestive. Under each heading there is a list of observable symptoms that may warrant referral to a specialist provider in that area.

The main heading says, “Feeding Assessment Referral Guide”. The main subheading says, “Use the following checklist during the feeding evaluation to observe symptoms that may warrant referral to specialists.”

Under gastrointestinal, the observable symptoms are:

- Frequent spitting up/vomiting during meal
- Fussiness, crying, or arching during meal
- Wheezing, stridor, cough, or hoarseness while eating
- Gagging during meal
- Burps frequently while eating
- Drools while eating
- Avoidance or prioritizing of certain food textures

Under aerodigestive, the observable symptoms are:

- Gets red in the face while eating
- Coughs during meal
- Food/liquid comes out nose while eating
- Gets tired and cannot finish eating
- Breathes harder/faster while eating
- Evidence of stridor v. stertor
- Needs to pause during meal to catch breath
- Watery eyes while eating

Under behavioral, the observable symptoms are:

- Refuses to eat
- Whines, cries, or tantrums during meal
- Insists on food being offered a specific way
- Throws or pushes food away
- Will not stay seated during meal
- Throws or spits food
- Parent has to do something special to get child to eat
- Parent and child have conflict during feeding
- The parent appears stressed and overwhelmed during feeding

Under nutrition, the observable symptoms are:

- Appears underweight
- Exclusion of entire food group
- Eating only one texture of food during evaluation

At the bottom, the checklist says, “If the child has demonstrated any of these signs/symptoms while eating, referral to a medical specialist, in addition to your treatment, may be warranted.”

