## 4 STUDY DESIGN

### 4.1 OVERALL DESIGN

This is a randomized crossover pilot study. It will be conducted online through one site, UNC Chapel Hill. The study intervention is the 'Clinical Feeding Tool' also known as the decision support tool. Our hypothesis is that clinicians will change their recommendations for feeding therapy and specialist referral when using the tool compared to when they do not use the tool. Clinicians will be randomly assigned to respond to either Case A or Case B without using the tool (2 groups). Then, they will respond to the other case using the tool. Total participation time is estimated at 20 minutes.

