## 5 STUDY POPULATION

### 5.1 INCLUSION CRITERIA

In order to be eligible to participate in this study, an individual must meet all of the following criteria:

1. Provision of signed and dated informed consent form
2. Stated willingness to comply with all study procedures and availability for the duration of the study
3. Male or female, aged 18 or older
4. Speech language pathologist or occupational therapist

5. At least 2 years of experience evaluating and treating pediatric feeding
6. Have worked in Early Intervention in the last 5 years
7. English proficiency
8. Currently reside in NC

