## 5.2 EXCLUSION CRITERIA

An individual who meets any of the following criteria will be excluded from participation in this study:

1. Less than 2 years of experience
2. Have not worked in Early Intervention in the last 5 years
3. Does not currently reside in NC

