#### 6.2.2 FORMULATION, APPEARANCE, PACKAGING, AND LABELING

The intervention is a checklist provided both within the body of a survey, and as a PDF.

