### 6.4 STUDY INTERVENTION COMPLIANCE

This study is a survey. Thus, as long as the participant completes the assigned survey, they will have adhered to the study protocol.

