# 8 STUDY ASSESSMENTS AND PROCEDURES

## 8.1 EFFICACY ASSESSMENTS

To test intervention efficacy, the participant will be asked to answer a set of clinical questions after reading the case study. They will first do this without the intervention and then read another case study using the intervention. This will be administered through Qualtrics in survey form.

The questions include:

- Would you recommend feeding therapy to this child? Yes/No
  - If yes, "With what frequency would you recommend therapy?"
    - 2 times per week, 1 time per week, Less than one time per week
  - If yes, "What therapy target areas might you include for this child?" (select all that apply)

- Oral motor skills, sensory, behavioral, medication, modification of food/liquid, modification of equipment (seating, utensils, etc.), modification of environment (location, distractions, routine, etc), parent coaching, other (fill in)
- If yes, "What would be the recommended length of treatment for this child?"
  - Less than 6 months, 6-12 months, More than 12 months
- What diagnosis would you give this child?
- Would you refer this family to any other providers/specialists for evaluation/treatment? Yes/No
  - If yes, "What other professionals would you refer this child to? Check all that apply."
    - Nutritionist/dietician, gastroenterologist, otolaryngologist (ENT), aerodigestive clinic, pulmonologist, occupational therapist, speech language pathologist, psychologist/social worker, applied behavior analyst (ABA), allergist, multidisciplinary feeding team, other (list)

In addition to the clinical questions, the following questions will be asked in order for the participant to evaluate the tool:

- With a likert scale of completely agree, agree, neither agree nor disagree, disagree, completely disagree
  - The Clinical Feeding Guide meets my approval
  - The Clinical Feeding Guide is appealing to me
  - I like the Clinical Feeding Guide
  - I welcome the Clinical Feeding Guide
  - The Clinical Feeding Guide seems fitting
  - The Clinical Feeding Guide seems suitable
  - The Clinical Feeding Guide seems applicable
  - The Clinical Feeding Guide seems like a good match
  - The Clinical Feeding Guide seems implementable
  - The Clinical Feeding Guide seems possible
  - The Clinical Feeding Guide seems doable
  - The Clinical Feeding Guide seems easy to use
- If you could make changes to the CFG you would (check all that apply):

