## 10 SUPPORTING DOCUMENTATION AND OPERATIONAL CONSIDERATIONS

### 10.1 REGULATORY, ETHICAL, AND STUDY OVERSIGHT CONSIDERATIONS

#### 10.1.1 INFORMED CONSENT PROCESS

##### 10.1.1.1 CONSENT/ASSENT AND OTHER INFORMATIONAL DOCUMENTS PROVIDED TO PARTICIPANTS

Consent forms describing in detail the study intervention, study procedures, and risks are viewed by the participant and documentation of informed consent is required prior to starting intervention/administering study intervention. The following consent materials are submitted with this protocol Online Consent form.

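### The plan neither protects the no-tool condition nor records use of the tool, so the difference between conditions may be diluted by an amount the trial cannot measure

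*Combined protocol and SAP*

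**What the plan says.** Tool status is set by position in the survey. Section 8.1 says of the clinical questions: "They will first do this without the intervention and then read another case study using the intervention". Section 4.1 agrees; what is allocated is which case is answered without the tool. Sections 3 and 9.4.2 then name the compared groups by use or non-use of the tool, separately for each case.

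**Who may enter.** The checklist came from Delphi work: "The study intervention is a checklist that was developed with feeding specialists at UNC Health through Delphi surveys". Section 5.1 admits an eligible discipline, "Speech language pathologist or occupational therapist", with feeding experience, recent Early Intervention work and North Carolina residence. Section 5.2 has three exclusions: too little experience, residence outside the state, and "Have not worked in Early Intervention in the last 5 years". Neither list mentions Delphi participation or prior sight of the checklist.

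**What is read before the no-tool case.** Section 10.1.1.1 says: "Consent forms describing in detail the study intervention, study procedures, and risks are viewed by the participant", with consent documented before the intervention starts. The schema in section 1.2 lists consent ahead of the survey.

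**What counts as use.** Section 6.1.2 has each provider view the checklist for one case. Section 6.4 says that "as long as the participant completes the assigned survey, they will have adhered to the study protocol". The question list in section 8.1 asks for opinions of the tool, but not whether it was used for the second case or was already familiar. Section 6.2.2 adds: "The intervention is a checklist provided both within the body of a survey, and as a PDF".

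**The concern.** A comparison of tool with no tool needs the no-tool answers to be given without the tool's content. It also needs some knowledge of whether the tool was used when it was supplied. The plan secures neither.

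A therapist who already knows the checklist answers the no-tool case partly informed by it. A consent form that set out the headings or items could do the same to every participant, because everyone reads it before the first case. In the second case, a therapist who scrolls past the checklist is still analysed as using it, and also rates its feasibility. Each of these can narrow the gap in recommendation percentages. Any Delphi member who enrolled would also be rating a tool they helped to build, which could raise the acceptability scores.

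What is at stake is interpretation. If the percentages barely differ, the reader cannot tell a tool that changes nothing from a contrast that was not delivered. Neither prior exposure nor use can be reliably reconstructed once the surveys are closed.

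**Working it through.** **The plan's own figure.** Sections 5.5, 6.3 and 9.2 give 14 SLPs and 14 OTs in each of two groups: 2 × (14 + 14) = 56. Each case is therefore compared as 28 v 28. The plan states no alpha, power, effect size or expected rates, so there is no power figure to reproduce and the dilution cannot be computed from the documents.

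**Model (all rates assumed).** Let d be the true difference in the percentage answering yes, p the rate without the tool, c the share of no-tool answers already informed by the tool, and m the share of tool answers given without using it.

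- Observed no-tool rate = p + c·d
- Observed tool rate = p + (1 − m)·d
- Observed difference = d × (1 − c − m)

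With d = 30 points:

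| c | m | d(1 − c − m) | d(1 − c)(1 − m) |
|---|---|---|---|
| 0 | 0 | 30 | 30 |
| 5% | 10% | 25.5 | 25.65 |
| 10% | 20% | 21 | 21.6 |
| 20% | 30% | 15 | 16.8 |

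The last column allows for a previously exposed therapist who skips the checklist but still knows its content, with exposure and non-use independent. It changes little at the lower rates.

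**Effect on the optional tests.** Assume 28 v 28, a two-sided 5% level (section 9.4.1 says two-tailed but gives no level) and true rates of 50% v 80%. Power is 66% without dilution, 47% at c = m = 10% (24 points) and 29% at c = m = 20% (18 points).

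**The Delphi route alone.** One panellist is 1/56 = 1.8% of the sample and sits in the no-tool group for one case only, where the share is 1/28 = 3.6%. On a 30-point difference that costs 30 × 1/28 = 1.1 points.

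**Where the formula applies.** It holds for yes percentages, which section 9.4.2 compares. It need not hold for agreement, which is how section 3 words the endpoints. Take pairwise agreement, p² + (1 − p)². At true rates of 20% v 80%, agreement is 0.04 + 0.64 = 0.68 in both groups, a difference of zero. If 20% of the no-tool group answer as tool users, their rate becomes 20 + 0.2 × 60 = 32%. Agreement is then 0.1024 + 0.4624 = 0.565, so the difference grows to about 0.115.

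**The case against.** A reader might infer that the contrast is diluted. The documents do not show that, and several objections stand.

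- **Panel overlap is possible, not shown.** Section 6.1.1 gives neither the panel's disciplines nor its size. A panellist would need to be an SLP or OT with recent Early Intervention work. Section 5.5 directs recruitment to contracted private practices and the Early Intervention system, although word of mouth is one channel. One panellist would matter little.
- **The consent form was not available for this review.** Section 10.1.1.1 is a general sentence. It does not establish that the headings or items are shown, and knowing that a referral checklist is under test is weaker than having its content. What remains is that the plan asks for detail and sets no limit on it.
- **Passing on the PDF is conjecture.** Nothing says when it is released or that anyone would share it. Equally, nothing says that first-case answers are locked before the checklist appears.
- **Non-use does not invalidate the comparison.** Tool provided v not provided is a valid contrast, and some non-use belongs to a tool's practical effect. The fault is the label and the missing record.
- **Dilution toward zero on all five recommendation endpoints does not follow.** The agreement example above shows an exception. Therapy frequency and targets are also asked only of those who recommend therapy.
- **This is a pilot sized by funding, reported mainly descriptively and with no power target.** The harm is an understated difference or an unclear null result, not the loss of a stated power.

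**Conclusion.** The point holds as a gap in safeguards. The plan analyses first-case answers as not using and second-case answers as using the tool, but leaves the no-tool condition open to prior knowledge and does not record use in the tool condition. The difference in recommendation percentages may be diluted by an amount the trial cannot measure.

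Any figure is illustrative: 30 points falling to about 21 at 10% prior exposure and 20% non-use. That assumes exposed therapists answer as if they had the tool and non-users as if they did not. If both shares are zero, nothing is lost. The documents support neither a claim that dilution has occurred nor one that it must affect every endpoint. Severity: consider. The changes are cheap, but must be in place before data collection.

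**What to change.** 1. **Section 5.2:** add the exclusion 'took part in the Delphi rounds or has previously seen the checklist', with one matching item in the existing interest survey.
2. **Section 10.1.1.1 and the survey build:** subject to IRB agreement, keep the checklist's headings, items and PDF out of the consent text. Show them only after first-case answers are submitted and locked.
3. **Sections 6.4 and 8.1:** add one item after the second case on whether the checklist was used, or offer optional tick boxes and store the ticks. Report the share who used it.
4. **Sections 3 and 9.4:** keep everyone who is otherwise analysed in the main analysis, and label the contrast 'tool provided v not provided'.

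The cost is a few Delphi members lost from the pool, a consent wording change needing IRB approval because it narrows the present call for detail, and one or two more survey items. Ticking may prompt slightly more engagement than viewing, which is why the ticks should be optional or replaced by a single question.

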#### 6.1.2 DOSING AND ADMINISTRATION

Each provider will view the checklist to use during one case study.

### 6.2 PREPARATION/HANDLING/STORAGE/ACCOUNTABILITY

#### 6.2.1 ACQUISITION AND ACCOUNTABILITY

The intervention is a checklist.

#### 6.2.2 FORMULATION, APPEARANCE, PACKAGING, AND LABELING

The intervention is a checklist provided both within the body of a survey, and as a PDF.

#### 6.2.3 PRODUCT STORAGE AND STABILITY

N/A

#### 6.2.4 PREPARATION

N/A

### 6.3 MEASURES TO MINIMIZE BIAS: RANDOMIZATION AND BLINDING

14 OTs and 14 SLPs will receive case A first; 14 OTs and 14 SLPs will receive case B first. There are two versions of the survey – one where case A is presented first and one where case B is presented first. Providers will be sent the link to the version to which they are assigned.

Assignment will be based on the order of study entry. For example, the first SLP to enroll will receive case A first, the second SLP to enroll will receive case B first, etc. Similarly, the first OT to enroll will receive case A first, the second OT to enroll will receive case B first, etc.

The PI will complete all randomization computations. There will not be blinding. Blinding is considered unnecessary in this case because the researchers will not have direct interaction with participants, participants will complete the full survey and intervention independently without interaction with the researchers.

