### 4.2 SCIENTIFIC RATIONALE FOR STUDY DESIGN

We have selected a crossover design for this pilot study in order to directly compare use of the tool to no use of the tool among a small group of participants. Therefore, participants will serve as their own control group. This was chosen given the varying experience of the participants with feeding.

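### The study is labelled randomized, but case order is set by strict alternation within discipline, and the PI who sends the survey links knows every next assignment

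*Combined protocol and SAP*

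**What the plan says.** Section 4.1 states the design twice: "This is a randomized crossover pilot study", and "Clinicians will be randomly assigned to respond to either Case A or Case B without using the tool (2 groups".

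Section 6.3 is the only place that says how assignment is done: "Assignment will be based on the order of study entry. For example, the first SLP to enroll will receive case A first". The second SLP gets case B first, and so on, with a separate but identical sequence for OTs. The planned numbers are 14 SLPs and 14 OTs in each order. There are two survey versions, and "Providers will be sent the link to the version to which they are assigned". The section adds: "The PI will complete all randomization computations. There will not be blinding". The reason given for not blinding is that researchers do not interact with participants.

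Section 5.5 describes the step before assignment: "If eligible and interested, they will provide their name and email". Then: "In the order of entry, the PI will email them a link to the survey".

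Section 4.2 justifies the crossover on the ground that "Therefore, participants will serve as their own control group". Section 8.1 has every therapist answer the first case without the tool and the second with it. Section 9.4.2 analyses each case separately.

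**The concern.** An A, B, A, B sequence with a fixed start is alternation, a quasi-random method. The protocol describes no random sequence, random start, block scheme or concealment, so the computations that section 6.3 gives to the PI contain no random element.

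One person also holds the entrant's name and email, knows the next order and sends the link that fixes it. The stated reason for not blinding, no contact with participants, concerns influence on responses. It does not address foreknowledge of the next assignment.

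Two things are at stake. First, the main comparison depends on how the groups were formed. No therapist answers the same case both with and without the tool, so the own-control argument in section 4.2 does not protect a per-case contrast. Second, section 10.1.11 commits the trial to registration and results submission, and section 5.4 refers to CONSORT. The word randomized would enter the public record for a study that, as written, is not randomized.

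**Working it through.** **1. The plan's own figure.** 2 disciplines x 2 orders x 14 = 56, which matches sections 5.5, 6.3 and 9.2. Section 9.2 bases the size on funding and equal groups, so there is no power calculation to reproduce.

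**2. What the rule produces.** Within each discipline, odd entry numbers get A first and even numbers get B first. Over 28 entrants this gives 14 and 14, by exactly one possible sequence. A random order with the same split could take any of C(28,14) = 40,116,600 sequences per discipline.

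**3. Predictability of the next assignment.** Under alternation it is 28 of 28 per discipline, or 56 of 56. For comparison, take someone who sees past assignments from a random list and always guesses the order with more places left. In a block of 2k the expected number of correct guesses is k + (2^(2k)/C(2k,k) - 1)/2. The documents give no block sizes; these are illustrations.

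| Method | Expected correct | Share |
|---|---|---|
| Alternation | 28 of 28 | 100% |
| Blocks of 2 (k = 1) | 1 + (4/2 - 1)/2 = 1.5 of 2 | 75% |
| Blocks of 4 (k = 2) | 2 + (16/6 - 1)/2 = 2.83 of 4 | 71% |
| One block of 28 (k = 14) | 14 + (268,435,456/40,116,600 - 1)/2 = 16.8 of 28 | 60% |

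A simulation of 20,000 runs gave 71% for blocks of 4 and 60% for a single block of 28. If the survey itself allocates, the sender does not choose the version at all.

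**4. Which groups are compared.** The tool goes with the second case.
- Case A: tool = B-first group, no tool = A-first group.
- Case B: tool = A-first group, no tool = B-first group.

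Both contrasts are between groups of 28 formed by the section 6.3 rule.

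**5. Effect of one exchanged pair (assumed for illustration).** Suppose one therapist says yes to both cases and another says no to both, with or without the tool. Move the first from A-first to B-first and the second the other way.
- Case A: (+1/28) - (-1/28) = +2/28 = +7.1 points.
- Case B: (-1/28) - (+1/28) = -2/28 = -7.1 points.
- Average of the two: 0. The plan contains no averaged analysis.

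**6. Chance variation for scale.** The SE of a per-case difference is sqrt(2p(1-p)/28), with the yes-rate p assumed: 8.0 points at p = 0.1, 12.2 at 0.3 and 13.4 at 0.5. Random allocation leaves this variation in place.

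**7. Cost of slight imbalance.** At 26:30 and p = 0.5, SE = 0.5 x sqrt(1/26 + 1/30) = 13.4 points, unchanged to one decimal.

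**The case against.** The strongest reply is that the label should be corrected but little else is at risk. Links go out in order of entry, therapists screen themselves online and answer alone, and nothing suggests the PI would know anyone's tendency to refer. Steering would mean breaking the entry order or misapplying eligibility, and a fixed rule can be audited against that order. Predictability is not a measure of bias. The exchanged pair is a constructed extreme, and its 7.1 points lie below the chance SE. This is a pilot with mainly descriptive reporting. Alternation balances discipline and entry time, and section 9.4.1 will assess experience and discipline as covariates. The larger problem, that the tool always comes second, survives any change of allocation.

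Much of this stands as a limit on size. No steering is shown, the room for it looks modest, and the percentages describe foreknowledge rather than distortion. It does not remove the contradiction. Descriptive reporting still presents tool and no-tool percentages as comparable. The baseline comparison in section 9.4.5 and the covariates in section 9.4.1 cover only measured factors and do not make an alternating sequence random. Order of entry limits steering only if it is followed, and the person trusted to follow it is the one who knows the sequence.

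**Conclusion.** The concern holds and should be corrected before anyone is allocated, because afterwards only relabelling is possible. Section 4.1 claims a design property that section 6.3 does not deliver: assignment is a fixed function of discipline and entry number, all 56 assignments are predictable, and there is no concealment from the person sending the links. That the PI knows each next assignment is an inference, but it follows directly from the rule and the PI's stated tasks. Strict alternation is the plain reading of the example in section 6.3, and no other section gives a different mechanism.

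Whether any steering would occur, and by how much, cannot be given from the documents. The 7.1-point shift rests on the assumed pair, and the 8.0 to 13.4 point SE on assumed yes-rates of 10% to 50%. Random allocation would justify the label and remove the foreknowledge. It would not separate the effect of the tool from that of being the second case read.

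**What to change.** In section 6.3, replace alternation with computer-generated random allocation, stratified by SLP/OT and aiming for 14:14 in each. Either route works:

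- **(a) Inside the survey:** one link, with balanced randomisation within discipline after the e-consent page. The two versions are merged, and discipline must be known or asked before the branch.
- **(b) Concealed list:** generated before the first entry and held by someone other than the person who sends the links.

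If alternation is kept, remove the claims of randomization from section 4.1 and describe the study as quasi-randomised alternation in the protocol, registration and reports.

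In either case, state that tool use is confounded with second presentation.

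Two smaller clarifications belong in the same edit:

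1. Section 7.2 allows replacements but gives no rule for their order. State that a replacement takes the next position on the list, and word the 14:14 figures in sections 6.3 and 9.2 as targets, since partial surveys are excluded (section 9.3) and small departures cost almost no precision.
2. Sections 1.2 and 1.3 place randomization before consent, whereas section 5.1 makes signed consent an eligibility criterion and section 7.2 speaks of consent and then randomization. Section 10.1.1.1 requires consent only before the intervention. Reconcile these; route (a) puts consent first.

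The cost is a few lines of text and a survey setting or a generated list, with no extra participants. Route (b) also needs a second person to hold the list.
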